2.0 OBJECTIVES

Our hypothesis is that change in ¹⁸F-FFNP uptake following 1-day of estradiol is a strong predictor of response to ET in patients with hormone-sensitive (ER⁺/± PgR⁺)/HER2- breast cancer. We believe the increase in tumor PgR after 1-day estradiol will be more reliable than a decrease after estrogen deprivation, particularly because most breast cancer patients are postmenopausal and basal PgR levels will be low due to the low endogenous, menopausal estrogen levels. Thus, we propose to use a hormone-challenge test for assessment of functional

ER based on the change in ^{18}F -FFNP uptake before and after a 1-day estradiol challenge in patients with ER+ metastatic breast cancer. We expect that the changes in ^{18}F -FFNP uptake to be a highly reliable means to predict a favorable response of ER+ breast cancer to ET. We propose to study patients with biopsy-proven new diagnosis of ER+ metastatic/recurrent breast cancer who are going to be treated with ET (tamoxifen, AI agents or faslodex) according to standard of care.

2.1. Evaluate whether the change in tumor uptake of ^{18}F -FFNP following a 1-day estradiol challenge differs among patients who respond to ET versus those who do not respond.

2.1.1 Determine the optimum cutoff value for change in tumor ^{18}F -FFNP uptake after estradiol to distinguish responders from nonresponders.

2.1.2 Evaluate whether the change in tumor uptake of FFNP can identify patients with hormone-sensitive disease who will respond to ET with greater sensitivity and selectivity than tumor PgR measured by IHC.

2.2 Evaluate the heterogeneity of tumor ^{18}F -FFNP uptake at baseline and after estradiol challenge in patients with multiple metastatic foci.

2.2.1. Explore whether response is related to ^{18}F -FFNP uptake heterogeneity. To assess the heterogeneity at the baseline, a comparison with FDG-PET/CT will be performed to map the metabolically active disease. Once the metabolically active disease is determined, FDG+/FFNP- will be considered as discordant lesions. At follow-up, the baseline FFNP-PET/CT will be correlated with follow-up FFNP-PET/CT to assess heterogeneity in response to estradiol.

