ratio. The SUV is widely used for assessment of regional tracer accumulation in oncological studies, is technically simple to perform, and makes imaging easier for the patient because longer dynamic imaging is not required. SUV is a decay-corrected measurement of activity per volume of tissue (nCi/mL) divided by the average activity per unit mass in the entire body. The absolute change and the percent change in uptake of ^{18}F -FFNP will be assessed semiquantitatively and correlated with the clinical and radiologic results and subsequently with the results of the clinical follow-up evaluation. In patients with multiple lesions, the uptake up to 5 most intense lesions seen on PET images will be determined and the overall average values for all of the known lesions also will be recorded. The changes in SUV and T/N between the baseline and post estradiol challenge FFNP-PET/CT images will be compared in responders and nonresponders. Volumes of interest (VOIs) will be drawn around the entire lesion with the knowledge of the location of the tumor. SUV_{max} will be determined within the VOI. In addition, a similar volume of interest will be drawn in a comparable normal tissue region. The T/N ratio will be calculated by dividing the SUV_{max} of the tumor by the average SUV of normal comparable tissue. The absolute change and the percent change in uptake of ^{18}F -FFNP will be assessed semi-quantitatively and correlated with the clinical and radiologic results and subsequently with the results of the clinical follow-up evaluation. In patients with multiple lesions, the uptake of up to 5 lesions, selected as the most intense lesions seen on PET, will be determined and the overall average values for all of the known lesions also will be recorded. In addition, in patients with multiple lesions, SUV_{max} and T/N ratio will be measured for all known measurable lesions to assess within-patient heterogeneity in ^{18}F -FFNP uptake. Considering the optimum cutoff value for ^{18}F -FFNP uptake that distinguishes responders from nonresponders, lesions will be classified as ^{18}F -FFNP+ for lesions with ^{18}F -FFNP uptake at or greater than the cutoff value and ^{18}F -FFNP- for lesions with ^{18}F -FFNP uptake below the cutoff value. The changes in SUV and T/N after treatment will be compared in responders and nonresponders. The results of the PET studies will not be provided to the patient or the treating oncologist (see above). Clinical follow-up will provide information on tumor response, which will then be correlated with the sequential PET results to determine if these are predictive of ultimate response to estrogen therapy.

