10.0 STATISTICAL CONSIDERATIONS

10.1 Study Objectives and Endpoints

The primary endpoints of the study are the change in ^{18}F -FFNP uptake following one-day of estradiol measured as the SUV, T/M and tumor-to-normal tissue ratio (T/N), and the response to ET among cancer patients (responders vs. non-responders). The secondary endpoint of the study is the immunohistochemical (IHC) determination of PgR status (PgR+ vs. PgR-) in ER+ breast carcinoma.

Study Design: This is a pilot study aiming to evaluate if response to ET of breast cancer can be predicated by the changes in tumor uptake of ^{18}F -FFNP after a one-day estradiol challenge test. The sampling method is non-random. The change of ^{18}F -FFNP uptake after estradiol will be correlated with responsiveness to ET. Additionally, an optimal threshold of the change in ^{18}F -FFNP uptake will be developed to differentiate therapy responding and non-responding patients. Also, the change in ^{18}F -FFNP uptake after estradiol challenge will be compared with the IHC determination of PgR status with respect to the prediction of ET responsiveness.

Accrual: The rate of accrual for the study is expected to be about 1 - 2 patients per month. It is expected that the accrual period of the study will be completed in 30 months with total 50 patients enrolled.

Power Analysis: It is estimated that the response rate to ET in the recruited patients will range from 20-50%. Using a 2-sided independent t-test with 80% power at a 0.05 significance level, a sample of 10 responders vs. 40 non-responders (i.e., 20% response rate) will allow us to detect a minimum of 101% SD between-group difference, where SD represents a pooled standard deviation of the ^{18}F -FFNP uptake changes among both therapy responding and non-responding patients; and a sample of 25 responders vs. 25 non-responders (i.e., 50% response rate) will allow us to detect a minimum of 80.9% SD between-group difference.

Data Analysis: Demographic and clinical characteristics of all the enrolled patients will be summarized using descriptive statistics. The changes in ^{18}F -FFNP uptake after estradiol challenge will be compared between responders and non-responders via

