Wilcoxon rank sum test. A receiver operating characteristic (ROC) curve will be plotted to identify an optimal threshold of ^{18}F -FFNP uptake change to determine a criterion for the future prediction of therapy responsiveness. The positive and negative predictive values (PPV and NPV) will be calculated for response to ET using both the ^{18}F -FFNP uptake-based criterion and IHC determination of PgR receptor status. Multivariate logistic analyses of therapy response will be used to examine prediction power among the changes in ^{18}F -FFNP uptake and PgR receptor status

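### The FFNP cutoff is tuned and scored in the same 50 patients while PgR IHC keeps a cutoff fixed in advance, so the objective 2.1.2 comparison is tilted toward FFNP

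*Combined protocol and SAP*

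**What the plan says.** Section 10.1 (Data Analysis) sets the cutoff from the study data: "A receiver operating characteristic (ROC) curve will be plotted to identify an optimal threshold of" FFNP change, to serve as a criterion for predicting response in future patients. The next sentence reads "The positive and negative predictive values (PPV and NPV) will be calculated for response to ET using both the" FFNP-based criterion and PgR status by IHC. Section 10.1 (Study Design) makes the comparison explicit: the change in "uptake after estradiol challenge will be compared with the IHC determination of PgR status with respect to the prediction of ET responsiveness". Objective 2.1.2 asks whether FFNP change identifies patients with "hormone-sensitive disease who will respond to ET with greater sensitivity and selectivity than tumor PgR measured by IHC".

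PgR positivity is defined in Section 3.1, item 3b, as an Allred score of 4 or more. The study is a single-centre pilot of 50 patients. No split sample, cross-validation, bootstrap correction, validation cohort or confidence interval is described for these accuracy figures.

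The FFNP variable is itself left open. Section 10.1 has the change "measured as the SUV, T/M and tumor-to-normal tissue ratio (T/N), and the response to ET among cancer patients". Section 6.5 adds that "The absolute change and the percent change in uptake of" FFNP will both be assessed. In patients with several lesions it measures up to five of the most intense, and "the overall average values for all of the known lesions also will be recorded". No primary measure and no definition of an optimal threshold is given.

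Section 10.1 also plans a Wilcoxon rank sum test of FFNP change, and closes with "Multivariate logistic analyses of therapy response will be used to examine prediction power among the changes in" FFNP uptake and PgR status.

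**The concern.** A cutoff chosen to separate responders from non-responders in a sample fits that sample's chance features as well as the real signal. Scored on the same patients, it looks better on average than it will in new ones. The PgR cutoff was fixed without reference to these outcomes, so its figures carry no such inflation. Setting the two side by side compares an optimistic estimate with an unbiased one, on the very question objective 2.1.2 poses.

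The unnamed uptake measure is a second possible source. Three indices in absolute and percent form give at least six candidates before any choice of lesion summary. If the best performer were picked after seeing response, that would add optimism which correcting the cutoff alone does not remove.

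At stake are a descriptive comparison that could report FFNP as better when it is not, and predictive values and a cutoff carried into later work that would disappoint there.

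**Working it through.** **Inputs.** From Section 10.1: 50 patients; response rate 20% to 50%, so 10 vs 40 up to 25 vs 25; two-sided 0.05, 80% power; detectable differences 1.01 SD and 0.809 SD. From Section 3.1: Allred 4 or more. *Assumed, because the documents do not say:* normal changes with equal SDs; cutoff at the maximum Youden index (J = sensitivity + specificity − 1); an IHC test independent of FFNP given response, with the same underlying separation, at its best fixed cutoff.

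**1. The plan's own figures.** The normal approximation is (1.960 + 0.842) × √(1/n₁ + 1/n₂):
- 10 vs 40: 2.802 × 0.3536 = 0.991
- 25 vs 25: 2.802 × 0.2828 = 0.792

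The noncentral t with 48 df gives 1.011 and 0.809, matching the stated 101% and 80.9% SD. These are minimum detectable differences, not expected effects. They are used below only as plausible values of d.

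**2. Optimism.** In each simulated trial, non-responders are N(0,1) and responders N(d,1), and c is the cutoff with the largest sample J. Apparent accuracy is read from the same 50 patients. True accuracy at that c, with p the response rate, is
- Se = 1 − Φ(c − d), Sp = Φ(c)
- PPV = p·Se / [p·Se + (1−p)(1−Sp)]
- NPV = (1−p)·Sp / [p(1−Se) + (1−p)·Sp]

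Means over trials:

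| | 10 vs 40, d = 1.01 | 25 vs 25, d = 0.809 |
|---|---|---|
| J, apparent vs true | 0.51 vs 0.35 | 0.42 vs 0.29 |
| PPV | 47% vs 38% | 73% vs 66% |
| NPV | 94% vs 90% | 73% vs 66% |

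Sensitivity and specificity, the measures objective 2.1.2 appears to mean, are inflated by about 13 and 3 points (10 vs 40) and about 6.5 points each (25 vs 25).

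**3. Head to head with IHC.** At its best fixed cutoff, d/2, the IHC test has true J = 2Φ(d/2) − 1 = 0.386 and 0.314.

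| FFNP leads / trails | 10 vs 40 | 25 vs 25 |
|---|---|---|
| On J, as planned | 70% / 25% | 68% / 24% |
| On J, both cutoffs fixed | 46–48% each way | 46–48% each way |

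On the planned measures, FFNP leads on both PPV and NPV in 53–54% of trials and IHC on both in 10%, against 39–40% each with no tilt. If neither test has any value, FFNP leads on J in 79–81%. At true effects of 2 to 3 SD it leads in 59–67% (no tilt: 42–48%). With a within-patient correlation of 0.5 between the tests it leads in 75% and 72%.

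**4. Other cutoff rules.** Mean PPV optimism (10 vs 40; 25 vs 25):
- closest point to (0,1): 6.6 and 4.8 points
- sensitivity at least 90%, then best specificity: 3.4 and 1.7 points
- specificity at least 90%, then best sensitivity: 3.8 and 3.2 points

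It is smaller than under Youden but positive each time.

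**5. Choosing the measure as well.** If the best of six equally informative measures (correlation 0.5 to 0.9) is picked on the data, apparent vs true J is 0.59–0.65 vs 0.36 (10 vs 40) and 0.48–0.53 vs 0.29–0.30 (25 vs 25). FFNP then leads in 80–90%.

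**6. The other planned analyses.** The Wilcoxon test uses no cutoff and is not affected by tuning it. In the logistic model with a useless FFNP, the likelihood-ratio test rejects at 5% in 6% of trials if FFNP is continuous, and in 22–23% if it is cut at the ROC threshold.

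**7. Does correction work?** Against an IHC test matched to FFNP's true accuracy, the uncorrected comparison favours FFNP 76%/20% and 73%/20%. After cross-validation it is 49%/50% and 47%/51%, so the correction does not tilt the comparison the other way. Ordinary bootstrap correction leaves 36–42% of the optimism. With six measures, cross-validating the cutoff alone leaves 50–59%; repeating both choices in each fold leaves about none.

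**The case against.** The strongest reply is that the plan names no ROC rule, so the Youden figures rest on an assumption, and a different rule can even change who leads. That is correct as far as it goes. With a rule requiring 90% sensitivity, FFNP leads on J in 51% and trails in 45% (10 vs 40), or 34% and 58% (25 vs 25); requiring 90% specificity gives 41%/55% and 36%/57%. These reversals arise because FFNP's cutoff is then placed away from its best J while the assumed IHC test sits at its own. FFNP's figures are still inflated on average under every rule tried. What stands is that the size, and the leader in a given comparison, depend on the rule. The bias is also an average: even under Youden, apparent PPV falls below its true value in about 12% of trials.

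Other points have some force. J is not a planned statistic, which is why PPV and NPV are shown as well. The plan does not say the best of several measures will be chosen, so step 5 is conditional; in addition, Section 6.5 describes SUV and T/N but not T/M. The logistic sentence refers to uptake changes and not to the criterion, so a continuous term is the more natural reading, but it is not stated.

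Finally, this is a pilot with no planned test of FFNP against IHC accuracy. Section 1.3 also shows the group carrying an earlier ROC-derived FDG cutoff into a later study, where PPV went from 100% (15 of 15) to 80% (95% CI 61% to 92%). The populations differed, so that fall is not all optimism. It shows awareness of the need to validate, but it does not correct the present analysis, and neither the predictive values nor the IHC comparison is labelled exploratory.

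**Conclusion.** The concern holds. Followed as written, the plan gives FFNP accuracy figures that are too high on average and sets them beside IHC figures that are not. Confidence is high for the direction of the average bias. Under the Youden rule and the plan's detectable differences, PPV is overstated by about 9 points (10 vs 40) or 7 points (25 vs 25) and NPV by about 4 or 7. Under the other rules tried, the PPV excess is about 2 to 7 points. All sizes assume normal data and one pre-chosen uptake measure; choosing the measure on the data would enlarge them. The Wilcoxon comparison and the power statement are unaffected. The harm is to a descriptive comparison and to a cutoff intended for later use, so this should be fixed but does not undermine the study.

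**What to change.** Amend Section 10 as follows.

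1. Name one uptake measure (index, absolute or percent change, lesion summary) and the ROC criterion. If the measure is to be chosen on the data, include that choice in the resampling.
2. Report FFNP sensitivity, specificity, PPV and NPV from an internal validation that repeats the whole selection in each resample, with intervals labelled approximate. Repeated stratified cross-validation is one option. Ordinary bootstrap correction helps, but removed only about 60% of the optimism in the simulations.
3. Report the same four measures for PgR IHC at Allred 4 or more. Base the comparison on the corrected figures, as paired within-patient differences with intervals. State that FFNP enters the logistic model as a continuous variable.
4. Label the cutoff and its uncorrected accuracy exploratory.

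The cost is one SAP paragraph and analysis code, with no new data. Reported FFNP accuracy will be lower, and the freedom to choose among SUV, T/M and T/N afterwards is given up. The comparison will also look imprecise: 1.96 SD of the corrected J difference across simulated trials is about 0.49 (10 vs 40) or 0.39 (25 vs 25). The pilot is therefore unlikely to show that FFNP beats IHC, and the report should say so.

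### Objective 2.1.2 asks for sensitivity and selectivity against IHC PgR, but section 10.1 names only PPV and NPV as accuracy measures for both tests

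*Combined protocol and SAP*

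**What the plan says.** Section 2.0, objective 2.1.2, asks whether the FFNP change can identify patients who "will respond to ET with greater sensitivity and selectivity than tumor PgR measured by IHC". I read selectivity as specificity.

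Section 10.1 returns to this comparison in four places:

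- The Study Design paragraph says that the FFNP change will be "compared with the IHC determination of PgR status with respect to the prediction of ET responsiveness". It names no measure, test or criterion for success.
- The Data Analysis paragraph says "A receiver operating characteristic (ROC) curve will be plotted to identify an optimal threshold of" FFNP uptake change. This curve is for FFNP only and serves to choose the cutoff.
- The next sentence says "The positive and negative predictive values (PPV and NPV) will be calculated for response to ET", using both the FFNP "uptake-based criterion and IHC determination of PgR receptor status".
- The last sentence says "Multivariate logistic analyses of therapy response will be used to examine prediction power among the changes in" FFNP uptake and PgR status.

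Section 10.1 does not list sensitivity or specificity for IHC PgR. It gives no paired comparison of the two tests and no interval for the contrast.

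Two other statements bear on the point. The Power Analysis paragraph expects that "the response rate to ET in the recruited patients will range from 20-50" percent. Section 3.1 fixes PgR positivity in advance at an Allred score of 4 or more.

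**The concern.** The objective and the analysis use different measures. Sensitivity and specificity condition on the outcome: what share of responders, and of non-responders, the test classifies correctly. PPV and NPV condition on the test result and also depend on how many patients respond. A reader of the planned output would see two PPVs and two NPVs and would have to work back to learn whether FFNP finds more responders than IHC does.

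At stake is a claim on 2.1.2. NPV is driven by the ratio (1 − sensitivity)/specificity, so a gain in specificity can offset a loss of sensitivity and leave NPV unchanged. FFNP could then be reported as better on PPV and no worse on NPV while missing more responders than IHC, so that the sensitivity half of 2.1.2 fails without being seen. Because the comparison has no named measure, the one to emphasise could also be chosen after the data are known.

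**Working it through.** **Inputs from the documents.** Response rate p of 20% to 50%, with group sizes 10 vs 40 and 25 vs 25 (10.1, Power Analysis). Prior FES-PET counts: 12 of 24 test-positive and 5 of 27 test-negative patients responded (1.3). The documents give no accuracy for IHC PgR or for FFNP change as predictors of response, so those values are assumed below.

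**The plan's own power figures.** A two-sample t-test (noncentral t, 48 degrees of freedom, two-sided 0.05, 80% power) gives detectable differences of 1.011 SD for 10 vs 40 and 0.809 SD for 25 vs 25. The stated 101% and 80.9% reproduce. They concern uptake change between responders and non-responders, and do not cover objective 2.1.2.

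**Formulas.** With sensitivity Se and specificity Sp:

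- PPV = Se·p / [Se·p + (1 − Sp)(1 − p)]
- NPV = Sp(1 − p) / [Sp(1 − p) + (1 − Se)p]

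**Predictive values and sensitivity are different answers.** The FES counts give PPV 12/24 = 50% and NPV 22/27 = 81%, as section 1.3 states. The same counts give sensitivity 12/17 = 71% and specificity 22/34 = 65%, at a response rate of 17/51 = 33%. With that sensitivity and specificity held fixed, PPV goes from 33% at p = 20% to 67% at p = 50%, and NPV from 90% to 69%.

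**A loss of sensitivity that NPV does not show** (assumed accuracies, 10 responders and 40 non-responders):

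| | Sensitivity | Specificity | PPV | NPV |
|---|---|---|---|---|
| IHC PgR | 8/10 | 16/40 | 8/(8+24) = 25.0% | 16/(16+2) = 88.9% |
| FFNP | 6/10 | 32/40 | 6/(6+8) = 42.9% | 32/(32+4) = 88.9% |

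FFNP gains 17.9 points of PPV, ties on NPV and loses 20 points of sensitivity. The tie does not depend on the response rate, because (1 − Se)/Sp is 0.2/0.4 = 0.5 for IHC and 0.4/0.8 = 0.5 for FFNP. At p = 50% NPV is 66.7% for both, and PPV is 57.1% vs 75.0%.

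**Where the masking fades.** It needs low IHC specificity.

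| Assumed Se/Sp, IHC vs FFNP | NPV at p = 20% | NPV at p = 50% |
|---|---|---|
| 90%/35% vs 60%/95% | 93.3% vs 90.5% | 77.8% vs 70.4% |
| 90%/50% vs 50%/95% | 95.2% vs 88.4% | 83.3% vs 65.5% |

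In the first row the fall is small at 20% response and plain at 50%. In the second it is visible at both.

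**Precision if sensitivity is reported.** The exact 95% interval is 44% to 98% for 8/10 and 59% to 93% for 20/25. Exact McNemar needs at least 6 discordant pairs, all in one direction, for p < 0.05 (2 × 0.5⁶ = 0.031; five of five gives 0.0625). With 10 responders that is a 60-point difference. Power for 90% vs 60% sensitivity (assumed) is about 5% to 8% with 10 responders and 57% to 81% with 25, depending on how the two tests' results overlap.

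**Effect of choosing the cutoff on the same patients.** I simulated a marker unrelated to response, with the cutoff maximising the Youden index (sensitivity + specificity − 1). That criterion is an assumption, since the plan names none. The mean apparent index is 0.20 for 10 vs 40 and 0.16 for 25 vs 25, where the true value is 0. IHC PgR has a cutoff fixed in advance and gets no such lift.

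**The case against.** Four arguments on the other side deserve weight.

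- **More than predictive values is planned.** A reader might infer that PPV and NPV are the whole comparison. They are not: the logistic analyses use both predictors, and the ROC curve shows FFNP sensitivity and specificity at every cutoff. This stands, but neither sets FFNP sensitivity or specificity beside that of IHC.
- **The answer can be recovered.** A reader might infer that the study cannot answer 2.1.2. Computing PPV and NPV for each test requires its 2x2 table against response, and that table contains sensitivity and specificity. This stands: it is a gap in planning and reporting.
- **Both tests face one response rate.** The swing of PPV and NPV over 20% to 50% matters for carrying results to other patients. It does not distort the head-to-head comparison in this cohort. This also stands.
- **PPV and NPV need not mislead.** A reader might infer that the plan would point the wrong way. In the 90%/35% vs 60%/95% case FFNP is the better overall discriminator (Youden index 0.55 vs 0.25), so a verdict in its favour is reasonable on that footing; only the sensitivity half of 2.1.2 fails. The masking also rests on assumed accuracies.

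The study is a self-described pilot, 2.1.2 is a sub-objective, and the background reports the earlier FDG and FES work by PPV and NPV. Keeping them is a coherent choice. None of this supplies the measure that the objective names.

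**Conclusion.** The concern holds as a mismatch between objective and analysis. Objective 2.1.2 is worded in sensitivity and selectivity. PPV and NPV are the only accuracy measures that section 10.1 names for both tests, so the planned output does not report the quantity asked for.

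In the tied-NPV illustration the consequence is a 20-point loss of sensitivity that NPV does not show, next to a PPV that rises from 25.0% to 42.9%. That size rests on assumed accuracies and on low IHC specificity; with higher IHC specificity NPV does fall. The documents do not support saying that the objective is unanswerable or that the planned comparison is bound to mislead. I also assume that selectivity means specificity. The change should be made, since it is cheap and uses data already planned.

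**What to change.** In section 10.1, Data Analysis:

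1. Make the 2.1.2 analysis the paired difference between the FFNP criterion and IHC PgR in sensitivity (within responders) and in specificity (within non-responders). Report both tests' values alongside the differences.
2. Give each difference a 95% interval that allows for the FFNP cutoff being chosen on the same data, for example by a bootstrap or cross-validation that repeats the cutoff selection. An ordinary interval would favour FFNP.
3. Keep PPV and NPV as secondary, quoted with the observed response rate, and state that superiority on 2.1.2 will not be claimed from them alone.
4. Label any McNemar p-value as descriptive.

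The cost is one paragraph and some programming, with no new data. The downside is wide intervals, especially near 10 responders, so the comparison will read as an estimate and not as a test.
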